#### 8.2. ABNORMAL LAB RESULTS

The following criteria should be used to determine whether laboratory results should be reported as adverse events:

- Accompanied by symptoms, and (or);
- Require further diagnostic examination or pharmacological/surgical intervention, and (or);
- Lead to study treatment modifications (out of protocol-specified dose modification) or;
- Considered to be an adverse event by the Investigator or Sponsor.

If any of the above criteria is not met, only the repeat test for abnormal findings is needed and it does not constitute an adverse event. Reporting error test results does not need to be reported as an adverse event.

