# 4.3.2. Dose-Limiting Toxicity

Definition of DLT: All toxicity or adverse events (AEs) are graded according to NCI-CTCAE 5.0. Any AE occurring during C1 (21 days) that is not clearly caused by something other than investigational drug:

Hematological toxicity:

- Grade 4 neutropenia that lasts for >7 days;
- Grade  $\geq$ 3 febrile neutropenia (ANC<1,000/mm^3, with a single temperature of  $\geq$ 38.3°C or a sustained temperature of  $\geq$ 38°C for more than one hour);
- Grade 3 neutropenia with infection;
- Grade 3 thrombocytopenia with clinically significantly bleeding;
- Grade 4 thrombocytopenia;
- Grade  $\geq$ 4 anemia

Non-hematological toxicity:

- Grade  $\geq$ 4 toxicity;
- Grade 3 toxicity that fails to be resolved to ≤Grade 2, with the exception of diarrhea, nausea and vomiting;
- Grade  $\geq$ 3 immune-related adverse event (irAE)
- Any Grade 3 tumor flare reaction (local pain, irritation or rash at known or suspected tumor focus) that lasts for 7 days or above;
- Grade 3 or Grade 4 non-hematological laboratory abnormalities, if meet any of the followings:
  - need medical intervention
  - require hospitalization
  - last for >7 days

and other toxicity of any grade that requires premature termination of the study as determined by the investigator and the sponsor through discussion.

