## 6.4. STUDY TREATMRNT ADJUSTMENT

These guidelines should be followed by clinical Investigators, however, for an individual subject, dose interruptions, reductions, and treatment discontinuation should also be based on the clinical circumstance. Deviation from these guidelines must be documented and communicated with the sponsor. Adverse events are to be graded according to NCI CTCAE version 5.0.

- For the Phase Ib dose escalation, dose reductions for BLU-554 during the evaluation period of DLTs are only allowed if a DLT is observed.
- Dose reduction is not permitted for CS1001. If a subject experience a CS1001 related toxicities, then the subject must suspend or permanently discontinue CS1001 treatment.
- During the study treatment, if Investigator can judge AE is associated with one of the investigation products, the IP can be suspended, another IP could continue to be administrate. If cannot judge, both of the IPs should be suspended.
- If the study treatment is delayed according to the scheduled administration time for any reason (BLU-554 interrupted 2 weeks, CS1001 interrupted 9 weeks), the study treatment will no longer continue to be given (if the investigator considers that the subject is still benefiting, the subject may continue to receive the treatment with the consent of the medical monitor, i.e. the sponsor).
- Two administration delays are allowed due to toxicity. If the need for third delayed

administration of toxicity occurs, after consultation with the sponsor, the study treatment will be permanently terminated.

- 6.4.1. BLU-554 Dose Modifications
  - Any Grade 1 or Grade 2 BLU-554-related AE no dose modification required
  - Any Grade 3 or Grade 4 BLU-554-related AE, suspend (for at most 2 weeks) until event is ≤ Grade 1, or has returned to baseline, then resume by reducing 1 dose level. (if returned to ≤ Grade 1 or baseline within 14 days, and Investigator believes that it is in the subject's best interest, treatment may resume without dose reduction, with the written approval of the sponsor). If not resolved or returned to ≤ Grade 1 or baseline within 14 days, subjects should discontinue the treatment with BLU-554.
  - After reducing the dose of BLU-554 due to BLU-554-related adverse events, subjects should maintain such reduced dose during the subsequent treatment. The dose can be reduced as low as 300 mg.

\* In case immune mediated etiology cannot be excluded; consider following the guidelines in Section 14.3.

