## 7.1.5. Laboratory Tests

The blood and urine samples used for clinical laboratory assessment will be collected as specified by the protocol. The specific collection time points are described in the SOA. Details of sample preparation and analysis will be provided by local laboratories. The reference ranges for all safety parameters will be provided by local laboratories.

This study will detect the following parameters;

Blood test	Platelet Count	Platelet Count		RBC Indices:		WBC count with Differential:		
	RBC Count		MCV		Neutrophils			
	Hemoglobin		МСН		Lymphocytes			
	Hematocrit				Monocytes			
			E		Eosinopl	Eosinophils		
					Basophil	S		
Serum Chemistry	BUN/Urea 	Pota	assium	AST ALT Alkaline phosphatase		Total and direct bilirubin		
	Creatinine	Sod	lium			Total protein		
	Glucose	Cal	cium			Albumin		
						Total cholesterol		
						Triglyceride		
CK-MB	CK-MB							
HBV, HCV  , HIV	HCV antibody, HBsAg and HIV antibody							
AFP	AFP							
Coagulation	PT, INR and aPTT							
Routine Urine Test	pH, Specific gravity, Glucose, ketones, WBC, protein							
Thyroid Function	FT3, FT4 and TSH							
immunogenicity	ADA level							
FGF19, PD-L1 expression	FGF19 IHC、PD-L1							
Pregnancy test 	β-hCG							

1. The detection of this test item for the same patient in the same study site should be consistent throughout the study.

2. Subjects with HBsAg positive will further assess HBV DNA test, subject with HCV antibodypositive will further assess HCV RNA test.

3. A serum pregnancy test should be performed for female subjects at Screening; thereafter, a serum or urine pregnancy test should be performed on every odd cycle (e.g. C3, C5).

As for unexpected clinical laboratory detection values or values with unknown cause, if the investigator judges them as clinically significant, they should be repeatedly detected within 24h and continuously followed up until the detection results return to their normal value range and/or a rational explanation is found for such abnormality. The clinical laboratory will clearly mark the detection values beyond the normal value range, and the principal investigator needs to judge whether these abnormal values are clinically significant one by one, record those clinically significant ones as AEs and elaborate their relationship with treatment.

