#### Abnormal Liver Function Tests

Abnormal liver function that meets the following conditions will be considered as SAE, which shall be reported by the investigator according to the SAE reporting process. If no other criteria are applicable, the important medical serious event criterion could be used for judgment.

- For subjects with normal baseline of AST and ALT and total bilirubin: Treatmentemergent AST or ALT ≥3 × ULN, total bilirubin ≥2 × ULN, ALP < 2 × ULN (or not available) with no evidence of hemolysis;
- For subjects with abnormal baseline ALT or AST or total bilirubin: Treatmentemergent AST or ALT  $\geq 2 \times baseline values and \geq 3 \times ULN$ , or  $\geq 8 \times ULN$ (whichever is smaller) with total bilirubin level increased by at least  $1 \times ULN$  from baseline or if the value reaches  $\geq 3 \times ULN$  (whichever is smaller).

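### Section 8.2 contradicts itself and four other sections on when a laboratory abnormality is an adverse event, so laboratory AEs may be recorded inconsistently or too seldom

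*Protocol*

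**What the plan says.** Protocol 8.2 sets the rule for reporting a laboratory result as an AE. It gives four criteria, numbered here in their order:

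1. "Accompanied by symptoms, and (or" (the bracket closes there);
2. a need for further diagnostic work-up or for drug or surgical intervention, again joined by 'and (or)';
3. "Lead to study treatment modifications (out of protocol-specified dose modification) or";
4. "Considered to be an adverse event by the Investigator or Sponsor".

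The next sentence denies AE status in these words: "If any of the above criteria is not met, only the repeat test for abnormal findings is needed and it does not constitute".

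Four other protocol sections bear on the same question:

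- **8.1** names abnormal laboratory results among its examples of AEs, does not require symptoms, and states that AEs comprise serious and non-serious events.
- **7.1.5** has the principal investigator judge each out-of-range value and "record those clinically significant ones as AEs and elaborate their relationship with treatment".
- **4.3.2** draws DLTs from AEs in Cycle 1. Its list includes Grade 4 thrombocytopenia and "Grade 3 or Grade 4 non-hematological laboratory abnormalities, if meet any of the followings", one of the three conditions being a duration of more than 7 days.
- **8.5.1**, under Abnormal Liver Function Tests: "Abnormal liver function that meets the following conditions will be considered as SAE", defined by transaminase and bilirubin thresholds.

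Section 6.4.1 also makes a treatment rule turn on AE status: "Any Grade 3 or Grade 4 BLU-554-related AE, suspend (for at most 2 weeks) until event is" Grade 1 or lower, or back to baseline.

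**The concern.** The connectors in the 8.2 list make any one criterion sufficient. The closing sentence makes any one unmet criterion disqualifying. Both cannot be followed. A site that takes the closing sentence at its word would treat an asymptomatic Grade 3 or 4 change in transaminases, bilirubin or platelets as needing a repeat test only. A site that works from 7.1.5 would record the same result as an AE if it judged it clinically significant.

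Incidence and severity of AEs are a primary endpoint in Phase Ib and a secondary endpoint in Phase II. Section 8.2 is part of the rule that decides what enters the AE data, at 20 planned sites. Laboratory findings are also among the commoner known toxicities of both drugs, so the affected class of event is not marginal.

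**Working it through.** There is no plan figure to reproduce. The check is one of logic and of passages set side by side.

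**Step 1. The closing sentence against the list.** Four criteria, each met or unmet, give 2^4 = 16 patterns. In 2^3 = 8 of them there are no symptoms.

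| Reading | Patterns that are AEs (of 16) | Of the 8 without symptoms |
|---|---|---|
| Literal: not an AE if any criterion is unmet | 1 (all four met) | 0 |
| Alternatives: not an AE only if no criterion is met | 16 − 1 = 15 | 8 − 1 = 7 |

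Under the literal reading criterion 4 has no force of its own: the investigator's or sponsor's judgement counts only when the other three criteria are also met.

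**Step 2. The parenthesis in criterion 3.** 'Out of' most naturally means 'outside', which would leave out abnormalities that lead only to a modification the protocol itself specifies. Section 6.4.2 requires a CS1001 delay for Grade 2 or higher drug-related AST, ALT or total bilirubin elevation, so such a delay would not count under criterion 3. On the alternatives reading, an asymptomatic case with no further work-up or intervention would then be an AE only through criterion 4. The wording does not settle this meaning.

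**Step 3. Two worked cases.**

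- *An asymptomatic Grade 3 ALT rise in Cycle 1 lasting more than 7 days, with no intervention.* 8.2 read literally: not an AE. 7.1.5: an AE if judged clinically significant. 4.3.2: meets a listed DLT condition, and DLTs are drawn from AEs. Even the alternatives reading of 8.2 does not make it an AE automatically, so changing the closing sentence alone does not align 8.2 with 4.3.2.
- *Asymptomatic ALT at 3 × ULN or more with total bilirubin at 2 × ULN or more, normal at baseline, ALP below 2 × ULN, no haemolysis.* 8.5.1: an SAE, hence an AE under 8.1. 8.2 read literally: not an AE.

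**Step 4. Which outputs are exposed.** SAP 3.5.3 builds the TEAE, Grade 3 and above, and related-TEAE tables from AE records. SAP 3.5.5 gives CTCAE shift tables for specific laboratory tests, liver-threshold summaries and listings of abnormal values. SAP 3.5.1 summarises dose adjustment of both drugs, and SAP 3.3.1 gives reasons for ending each drug. Causality is collected per AE (protocol 8.4.4 and 8.4.6), so an abnormality with no AE record has no relatedness assessment anywhere.

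**Step 5. How common the class of event is.** Protocol 2.4.1.1, BLU-554 alone: related ALT increase 38/115 = 33%, AST increase 33/115 = 29%. Protocol 2.4.1.2, CS1001 alone, 29 subjects: anaemia 48.3%, proteinuria 44.8%, bilirubin increase 27.6%, ALT increase 24.1%.

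**The case against.** The strongest reply is that nobody would apply the closing sentence as it stands. It empties criterion 4 of meaning and looks like a slip for 'none'. Sections 8.1, 7.1.5 and 8.5.1 all point sites towards recording. The safety information also survives elsewhere: laboratory grades in SAP 3.5.5, dose changes in SAP 3.5.1, reasons for ending treatment in SAP 3.3.1. DLT evaluation is a separate scheduled item at the Cycle 1 visits in protocol 7.5.2. Data queries are governed by a Data Management Plan (protocol 9.2) that is not among the documents and may already match laboratory values to AEs.

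Much of this stands, and it rules out several stronger readings that a reader might infer:

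- *That sites will omit asymptomatic laboratory toxicity.* Three sections tell them otherwise, so the documents support a risk of inconsistent or low recording, not a certainty.
- *That discontinuation and dose reduction depend on AE recording.* They are also summarised outside the AE data.
- *That 8.2 and 6.4.1 form a closed circle in which a hold can never be triggered.* Section 7.1.5 confers AE status without reference to any hold.
- *That the number of subjects affected can be had by applying the 33% ALT rate to 40 Phase II subjects and an assumed asymptomatic share.* The 33% is an any-grade monotherapy rate in a study where most AEs were Grade 1 or 2. The documents give no asymptomatic share, and the 40 include an IHC-negative group that may not open. Mild rises needing no action would stay outside the AE data after the fix unless someone judged them AEs.

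The reply does not remove the defect. The documents do not say that 'any' is a slip, section 8 requires all participants to know its content, and relatedness is not recovered by any laboratory or dosing table.

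**Conclusion.** The rule in 8.2 is wrong as written. Its closing sentence contradicts its own list and conflicts with 8.1, 7.1.5, 4.3.2 and 8.5.1. The criterion 3 parenthesis is ambiguous and may exclude abnormalities handled by protocol-specified modification. The consequence is a risk of inconsistent or under-recorded laboratory AEs, with relatedness as the main loss that no other output recovers.

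The size is known only as logic: 1 AE pattern of 16 against 15, and 0 of 8 asymptomatic patterns against 7. The effect on reported rates depends on how sites read the sentence, which the documents do not show. The Phase II primary endpoint, ORR, is untouched. Phase Ib recruitment closed on 20 May 2020 and the RP2D was confirmed on 18 June 2020 (protocol 4.3.1), so for DLTs new wording comes too late and only a retrospective check helps. Nothing in the documents shows that a DLT was missed or that the RP2D is unsound.

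**What to change.** - In 8.2, reword the closing sentence so that a result is excluded only if *none* of the criteria is met.
- State plainly what the criterion 3 parenthesis means, or remove it.
- Reconcile 8.2 with 8.1, 7.1.5, 4.3.2 and 8.5.1 by cross-reference, so that a laboratory abnormality meeting a DLT condition or the liver-test SAE thresholds is an AE by definition. Reconcile the AE trigger in 6.4.1 with the same text.
- Carry the wording into the eCRF completion guidelines.
- List existing laboratory values of Grade 3 and above, including Phase Ib Cycle 1, and query those with no matching AE record, unless the Data Management Plan already does this.

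The cost is a few lines of protocol text, a guideline update and some queries. Reported AE rates may rise slightly.

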## 8.3. DEFINATION OF A SERIOUS ADVERSE EVENT

An SAE is any event that meets any of the following criteria as per the ICH definition:

- Death.
- Life-threatening ("life-threatening" means that the subjects are exposed to the risk of death in the event rather than the case it may theoretical lead to death in more serious event.)
- Inpatient hospitalization or prolongation of existing hospitalization (the reason for this condition is due to adverse events rather than the elective surgery, non-medical reasons, etc., as described below).
- Persistent or significant disability/incapacity.
- Causing congenital malformations or birth defects in offspring (congenital malformations or birth defects in the offspring of the subject);
- Significant medical events.

Important medical events that may not necessarily result in death, be life-threatening or require hospitalization may be considered as an SAE when, based upon appropriate medical and scientific judgment, they may jeopardize the subject and may require intervention measures to prevent one of the outcomes listed in this definition.

Examples of such events are: Intensive treatment in an emergency room or at home for allergic bronchospasm; Blood abnormalities or convulsions that do not result in inpatienthospitalization; Development of drug dependency or drug abuse. If the investigator considers that clinical symptoms and signs of an adverse event have a clinically significant impact, the AE is classified as a serious adverse event. Important medical events assessed by medical data and clinical experience of the investigator should be handled with reference to expedited reporting of serious adverse events. In addition, any suspected transmission of an infectious substance potentially via a medicinal product is also considered as an important medical event.

## **Unlisted (Unexpected) Adverse Event**

Unlisted adverse events refer to those whose nature or severity does not correspond to the reference safety information of the respective medicinal product. For investigational medicinal products, the expectedness of an adverse event will be judged on the basis of whether they are listed in the Investigator's Brochure. For comparator products approved for marketing, the expectedness of an adverse event will be judged on whether it is listed in the package leaflet.

#### Hospitalization

Adverse events leading to hospitalization or prolonged hospitalization during the study are classified as serious adverse events. Any new hospitalization in medical institutions (even if the hospital stay is less than 24 hours) meets the criteria. Hospitalization also includes intra-hospital transfer to an urgent/intensive care unit (e.g., from pediatrics to the medicine, medicine to the intensive care unit for coronary heart disease, and from neurology department to the TB ward, etc.).

The hospitalization in following institutions is not included:

- Rehabilitation;
- Hospice care;
- Short-term care (e.g. nursing care);
- Professional nursing;
- Home care;
- Admission to the general emergency department;
- Surgery on the same day (outpatient/ day surgery/ day-to-day operation).

Hospitalization or prolonged hospitalization due to following reasons is not a serious adverse event:

- Hospitalization that is not associated with a new onset of an adverse event or exacerbation of a pre-existing AE (e.g., an examination of pre-existing ongoing laboratory abnormalities);
- Hospitalization for a non-medical reason (e.g., the subject is homeless);
- Transactional hospitalizations (e.g., annual physical examinations);
- Study protocol-specified hospitalization (e.g., for procedures required by the study protocol);
- Voluntary hospitalization not leading to clinical adverse events (e.g. for elective cosmetic surgery);
- Pre-scheduled hospitalizations or procedures (Entire study protocol and (or) pre-planned treatments or procedures by subjects should be documented in the baseline files);
- Hospitalization only for the use of study medication.

Diagnosis and therapeutic non-invasive and invasive procedures, such as surgery, should not be reported as adverse events. However, the disease treated by such procedures should be reported as an adverse event if it meets the definition of an adverse event. For example, acute appendicitis that occurs during the adverse event reporting period should be reported as an adverse event and the appendectomy procedure to treat this disease should be recorded as the treatment of the adverse event.

#### 8.4. DOCUMENTATION OF ADVERSE EVENTS

All AEs spontaneously reported by subjects or answered by them after an open-label question "Do you have any health problem from the last visit/asking a question to the present?" by the investigator, or AEs observed should be collected and recorded. When collecting AE data, it is preferable to record the diagnosis (if possible) rather than to record a series of signs and symptoms. However, if a diagnosis is known, and the subject still has other signs or symptoms not belonging to the diagnosis, each symptom or sign should be recorded separately.

## 8.4.1. Time of AE Collection

AEs and SAEs will be collected from time of signature of main informed consent, throughout the treatment period and including the follow-up period.

Documentation of AEs and SAEs from time of signature of informed consent through the first dose of study drug is described in the electronic case report completion guidelines (eCCI).

Note: If the investigator gets known of any SAEs (including deaths) after the subjects have completed the safety follow-up or withdrawn from the study, the investigator should inform the sponsor's Pharmacovigilance team or representatives if, in his/her discretion, there is a reasonable possibility that such event is possibly correlated with the investigational drug.

## 8.4.2. Follow-up of Unresolved Adverse Events

During the course of the study all AEs and SAEs should be proactively followed up for each subject. Every effort should be made to follow up until all events are resolved, even though the event still exists after the discontinuation of treatment or termination of the study. As indicated medically, the investigator should follow up any AE that is not resolved at last visit by investigator.

The sponsor retains the right to request additional information for any subject with ongoing AE(s)/SAE(s) at the end of the study, if judged necessary.

#### 8.4.3. Events that Occur after Subject Withdraws from Study

After the subject has been permanently discontinued from the study, there is no obligation for the investigator to actively report information on new AE or SAEs occurring after the safety follow-up period. However, if an investigator learns of any SAEs, including death, at any time after the subject has been permanently discontinued from study, and he/she considers there is a reasonable possibility that the event is related to the investigational product, the investigator should notify the sponsor PV group or its representative.

#### 8.4.4. Variables collected

The following variables will be collected for each AE:

- AE (verbatim)
- The date when the AE started and stopped
- Change of CTCAE grade
- Whether the AE is serious or not
- Investigator causality attribution against the Investigational Product
- Action taken with regard to investigational product
- Administration of treatment for the AE
- Outcome

In addition, the following variables will be collected for SAEs:

- Date AE met criteria for serious AE
- Date investigator became aware of SAE
- AE is serious due to
- Date of discharge (if applicable)
- Probable cause of death (if applicable)
- Date of death (if applicable)
- Autopsy performed (if applicable)
- Causality assessment in relation to study procedure(s)
- Causality assessment in relation to other medication
- Description of SAE

